10.2.1 Overview of Treatment-Emergent Adverse Events

An AE overview summary table will be prepared including the number of subjects reporting an AE, the percentage of subjects with an AE, and the number of events reported, for the following categories:

- Unanticipated adverse device effect
- Any TEAEs
- Device related AEs
- Procedure related AEs

- Deaths
- Serious adverse events (SAEs)
- Device related SAEs
- Procedure related SAEs
- AEs leading to secondary surgical interventions

The relationship to device or procedure will be

10.2.2 Incidence of Adverse Events

AEs will be summarized by SOC sorted alphabetically and PT sorted in decreasing frequency of occurrence. Tables will display the total number of subjects reporting an AE, the percentage of subjects with an AE, and the number of events reported.

Summary tables will be prepared for:

- Unanticipated adverse device effect
- Any TEAEs
- Common TEAEs with an incidence of >5% in any treatment group
- TEAEs by severity
- Device related AEs
- Procedure related AEs
- SAEs
- Device related SAEs
- Procedure related SAEs
- AEs leading to secondary surgical interventions

Supporting data listings will be provided for:

- Unanticipated adverse device effect
- Any TEAEs
- Device related AEs
- Procedure related AEs
- Deaths
- Serious adverse events (SAEs)
- AEs leading to secondary surgical interventions

10.3 Secondary Surgical Intervention

Numbers and percentages of subjects who required any secondary surgical interventions as well as each type of the secondary surgical intervention (revision, removal, reoperation, or supplemental fixation) will be summarized.

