### 9.7.3 Other Safety Variables

Descriptive statistics of subsidence, device migration, nonunion, osteolysis and/or heterotopic ossification in the area surrounding the implant site by radiographic assessment, clinical laboratory testing and antibody monitoring will be presented for the safety analysis set by treatment group.

Number and percentage of subjects reporting the following events will be summarized:

- Any secondary surgical interventions including revisions, removals, reoperations, or supplemental fixations
- Secondary surgical intervention related to the graft material including revisions, removals, reoperations, or supplemental fixations

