Surgeries will be performed by board-certified/board eligible orthopedic surgeons. Perioperative prophylactic antibiotics will be administered before surgical incision in accordance with investigational site guidelines. Standard anesthesia procedures will be used. Standard surgical technique will be employed to gain access to each fusion site and to ensure rigid fixation of the fusion site. The joint will be exposed and prepared as per standard practice. The graft material should be placed in the joint space to minimize the chance of extrusion while maximizing bone-on-bone contact. Once the graft is placed, internal fixation screws will be placed across the joint. Up to three (3) screws can be used per joint. Supplemental pins and staples may be used, as well as supplemental screws and plates external to the fusion site(s). The surgical site will be closed in layers using standard surgical technique.

The trial is designed as a randomized, controlled trial comparing AMPLEX to ABG for bone fusion at 52 weeks. Although the primary efficacy endpoint will be assessed at 52 weeks, all subjects will be followed up for 78 weeks for the safety assessment. Post-discharge clinical visits will include

visits at 2, 6, 12, 24, 52 and 78 weeks. Adverse event data will be collected from randomization until the final follow up. The schedule of assessments is described in [Appendix 3](#).

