3.2 Determination of Sample Size

Assuming true success rates of the primary endpoint to be 60% for ABG and 62% for AMPLEX groups, respectively, 396 subjects are needed to maintain 85% power to demonstrate non-inferiority of AMPLEX to ABG with a non-inferiority margin of -12% (AMPLEX minus ABG) at a type I error rate of 1-sided 5% in a 2:1 randomization (264 for AMPLEX and 132 for ABG). To maintain this sample size for the 78-week completers (per the FDA's recommendation) after taking account for approximately 15% discontinuation (including lost to follow-up) rate, a total of 480 subjects (320 for AMPLEX and 160 for ABG) will be randomized.

In this calculation, the true success rate for AMPLEX is assumed to be slightly higher than that for ABG because of the potential benefit for AMPLEX on the absence of significant graft harvest site pain component. The assumption on the true success rate for ABG is made based on the clinical endpoint results in DiGiovanni et al. (2013)¹ ([1](#)) and the Augment SSED (2015) ([4](#)). These data indicate relatively high success rates for each component at Week 52. The estimated success rate as a composite endpoint is approximately 60%, when it is assumed that the success of each component is independent of each other.

4 Subject Disposition

All subjects who signed the informed consent form will be considered screened for the trial. All screened subjects who discontinued from the trial prior to randomization will be classified as screening failures. Screening failures and their primary reason for screening failure will be tabulated. The number of screened subjects will be used as the denominator when the percentage of each primary reason for screening failure is calculated.

Subjects who were randomized, received the procedure (surgery), were treated with the graft material, prematurely discontinued from the study, and completed the study will be tabulated with the reason of premature discontinuations for all randomized subjects. Similar tabulations will be made by investigational site and by region (US or Canada).

The number and percentage of subjects who attended Visits 2, 3, 4, 5, 6, 7, and 8 will be tabulated for all randomized subjects based on the nominal visit data recorded on the eCRF.

The time from randomization to discontinuation will be summarized by the Kaplan-Meier method.

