6.4 Safety Analysis Set

The safety analysis set will consist of all treated subjects (i.e., received AMPLEX or ABG). Analyses for the safety analysis set will be conducted according to the actual treatment received.

7 Trial population

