10.1 General Considerations

Safety parameters will be evaluated for the safety analysis set, and the data will be reported according to actual graft material received.

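### Secondary surgical interventions are planned only as crude percentages over a 78-week follow-up with about 15% expected loss, which modestly understates the risk

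*SAP*

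**What the plan says.** Secondary surgical intervention (revision, removal, reoperation or supplemental fixation) is a named safety endpoint in Protocol 2.2.3 and SAP 2.2.4. SAP 10.3 summarises it as "Numbers and percentages of subjects who required any secondary surgical interventions as well as each type of the secondary surgical intervention". Protocol 9.7.3 takes the same approach, with a number and percentage of subjects for "Any secondary surgical interventions including revisions, removals, reoperations, or supplemental fixations".

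SAP 10.3 states neither a denominator nor a time horizon. Both come from elsewhere:

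- **Denominator.** SAP 10.1 says: "Safety parameters will be evaluated for the safety analysis set, and the data will be reported according to actual graft material received". SAP 6.4 defines that set as everyone who received either graft, whatever their length of follow-up.
- **Horizon.** SAP Section 3 says "all subjects will be followed up for 78 weeks for the safety assessment".
- **Expected loss.** SAP 3.2 sizes the trial so that enough subjects complete 78 weeks "after taking account for approximately 15% discontinuation (including lost to follow-up) rate".

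The SAP uses Kaplan-Meier once, in Section 4: "The time from randomization to discontinuation will be summarized by the Kaplan-Meier method". Neither document plans a time-to-event, exposure-adjusted or completer-based estimate for secondary surgical interventions.

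**The concern.** A secondary surgical intervention can happen at any time up to Week 78. If a subject leaves at Week 30 and is reoperated at Week 50, the trial will generally not learn of it, but the subject still counts in the denominator as someone without an intervention. The percentage in the table is then the proportion with an observed intervention. A reader will tend to take it as the 78-week risk, and as an estimate of that risk it is too low.

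The primary composite does not fill the gap. It counts only interventions intended to promote fusion, and only up to Week 52. Other reoperations, and everything after Week 52, rest on this safety table. For a pivotal device trial, the risk of further surgery by a stated time is a figure that clinicians and regulators will want to read directly.

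**Working it through.** **1. The plan's own figures.** Inputs from SAP 3.2: success rates 60% (ABG) and 62% (AMPLEX), margin 12 points, one-sided 5%, power 85%, allocation 2:1.

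ABG n = (1.645 + 1.036)² × [0.60×0.40 + (0.62×0.38)/2] / (0.12 + 0.02)² = 7.19 × 0.3578 / 0.0196 = 131.2, rounded up to 132. With 264 on AMPLEX the total is 396, and the power is 85.2%. This reproduces the plan.

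For loss, 396/0.85 = 466. The stated 480 leaves 480 × 0.85 = 408 completers, or tolerates 1 − 396/480 = 17.5% loss. So about 15% loss by Week 78 is the sponsor's own planning value.

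**2. What the crude percentage estimates.** Let R be the true 78-week risk, F(t) the cumulative risk at time t, and G(t) the proportion still followed at t. With all treated subjects in the denominator and dropout unrelated to intervention risk:

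crude = ∫ G(t) dF(t), from 0 to 78 weeks.

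Because G(t) lies between 1 − d and 1, where d is dropout by Week 78, the crude figure lies between R(1 − d) and R. With constant event and dropout rates it becomes

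crude = a/(a + b) × [1 − (1 − R)(1 − d)], where a = −ln(1 − R) and b = −ln(1 − d).

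For R = 10% and d = 15%: a = 0.1054, b = 0.1625, and crude = 0.1054/0.2679 × (1 − 0.90×0.85) = 0.3933 × 0.235 = 9.24%.

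**3. Size within one arm.** The documents give no intervention rate, so R is an assumption, varied from 5% to 20%. Crude percentages at 15% dropout:

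| True R | Constant event and dropout rates | 75% of interventions by Week 12, constant dropout | Interventions only in Weeks 24–78, constant dropout | Interventions only in Weeks 24–78, all dropout by Week 12 |
|---|---|---|---|---|
| 5% | 4.62 | 4.84 | 4.50 | 4.25 |
| 10% | 9.24 | 9.69 | 9.00 | 8.50 |
| 15% | 13.88 | 14.53 | 13.49 | 12.75 |
| 20% | 18.52 | 19.37 | 17.99 | 17.00 |

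**4. Size between arms.** The true risk is set to 10% in both arms and overall dropout to 15% under 2:1 allocation. The splits are assumptions. The difference is AMPLEX minus ABG in percentage points, at constant event rate, with the range over the three event timings (dropout at a constant rate):

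| Dropout AMPLEX / ABG | False difference | Range |
|---|---|---|
| 15% / 15% | 0 | 0 |
| 18% / 9% | −0.46 | −0.20 to −0.61 |
| 20% / 5% | −0.77 | −0.32 to −1.02 |
| 12.5% / 20% | +0.39 | +0.17 to +0.52 |
| 10% / 25% | +0.79 | +0.33 to +1.04 |

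Standard error of the difference with 320 and 160 subjects: √[0.10 × 0.90 × (1/320 + 1/160)] = 2.90 points. At R = 5% the largest false difference over these splits was 0.52 points against a standard error of 2.11. At R = 20% it was 2.07 against 3.87.

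**5. Does a time-to-event estimate remove it?** In 4,000 simulated trials of the 20% / 5% case (R = 10%, no deaths), the crude AMPLEX figure averaged 8.97% and the crude difference −0.82 points. Kaplan-Meier averaged 9.99% and −0.05 points.

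**The case against.** The strongest case against is that this is a matter of presentation in a descriptive table. Safety endpoints carry no test, the protocol itself asks for counts and percentages, and the SAP follows it. Interventions intended to promote fusion enter the primary composite, which has missing-equals-failure, multiple imputation and tipping-point analyses (SAP 9.2.2). A careful reader would also have length of follow-up by category (SAP 8.1.1), time to discontinuation and a listing of discontinued subjects with their last visit (SAP Section 4), and narratives giving the type and timing of each intervention (Protocol 8.1). All of this stands, and it limits the point to a minor one. None of it yields a risk at a stated time, because these items are not linked to the intervention percentages.

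A reader might infer three stronger things that the documents do not support:

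- **That everyone who leaves early is counted as free of intervention.** An intervention before the subject leaves is counted, and Protocol 9.9 reports the available safety data of withdrawn subjects. If most interventions are early, a true 10% shows as 9.7%.
- **That the arm losing more subjects will look safer.** This needs unequal dropout. Subjects do learn their graft after surgery (Protocol 3.4.3 and 14.6), so an imbalance is possible, but neither document predicts one. With equal dropout neither arm is favoured.
- **That Kaplan-Meier curves by intervention type are the remedy.** The types compete with one another. At an assumed 10% risk, ABG would have about 0.10 × 160 = 16 events spread over four types. Censoring the other types would overstate each risk, and the curves would be nearly empty.

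Two smaller objections also stand. The 15% applies to randomized subjects and may include some who are never treated, so loss within the safety set may be lower. A time-to-event estimate also rests on an assumption of its own, that censoring is unrelated to intervention risk.

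**Conclusion.** The point holds as a small improvement. SAP 10.3 as planned modestly understates the 78-week risk of secondary surgical intervention. With 15% dropout unrelated to that risk, the shortfall is at most 15% in relative terms and about 7.5% if event and dropout rates are constant. An assumed true 10% would appear as 8.5% to 9.7%.

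The arm comparison is distorted only if dropout differs by arm. At an assumed 10% risk and the larger imbalances tried (20% / 5% and 10% / 25%), the distortion was about 0.3 to 1.0 points, well below the standard error of 2.9 points. In every case tried, at risks from 5% to 20%, it was smaller than the standard error.

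The non-inferiority conclusion does not depend on this table. The intervention rates and the dropout splits are assumptions; the 15% overall loss and the 78-week horizon are the documents' own.

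**What to change.** Keep the counts and percentages by type in SAP 10.3, state their denominator, and add for the safety set, by graft received:

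- the cumulative incidence of the first secondary surgical intervention of any type, counted from the date of surgery, with death as a competing event and censoring at last contact;
- estimates at Week 52 (Day 365) and Week 78, with numbers at risk, the arm difference and its 95% CI;
- a rule for the Week 78 visit window. That visit is due on Day 547 ± 30, so a subject who completes on Day 517 (547 − 30) is censored before Day 547. Reading the Week 78 estimate at Day 517, and labelling it so, avoids a thin risk set.

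Do not add time-to-event curves by type. State that the estimate assumes censoring unrelated to intervention risk, and show it beside the planned summary of time to discontinuation.

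The cost is one descriptive table. Protocol 8.1 already asks for the timing of each intervention, and SAP 9.2.1 needs dates for interventions intended to promote fusion, since it counts them up to the actual visit date. Neither document shows a dated case report form field for every type of intervention, so the sponsor should confirm that one exists. No change to design, sample size or testing is needed.

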10.4 Radiographic Assessment

All radiographic images will be assessed by independent image core laboratory. It will include radiographic assessment of subsidence, device migration, nonunion, osteolysis and/or heterotopic ossification in the area surrounding the implant site. Further details of these assessments will be specified in the Radiographic Evaluation Protocol.

10.4.1 Image Quality

Overall assessments of fusion site visualization on CT and X-ray will be summarized at each visit.

10.4.2 Post-operative Fusion Site

Pre-existing bone abnormality and adequacy of graft fill within the fusion site from the first post-operative (baseline) CT will be summarized for each treated joint.

10.4.3 Safety

Overall hardware condition, abnormal bone changes, graft integrity, graft migration or misplacement, and non-union from CT and X-ray will be summarized for each treated joint (except for overall hardware condition) at each visit.

10.5 Anti-B2A Antibody

Numbers and percentages of subjects with anti-B2A antibodies at screening, 6 weeks, and 12 weeks will be summarized. If a subject had a positive test at 12 weeks, subsequent test results will be presented in a listing.

10.6 Safety Laboratory Variables

Baseline for all laboratory analyses will be the values obtained at the last assessment prior to the surgery. Treatment-emergent laboratory data will include tests completed after the initiation of the surgery.

Safety laboratory variables will be grouped under “Hematology” and “Chemistry”.

10.6.1 Summary Statistics

Observed values and changes from baseline for the last post-baseline values will be presented for each laboratory variable. In addition, descriptive statistics will be presented for observed values and change from baseline at each time-point for each laboratory variable.

10.6.2 Laboratory Variable Changes Relative to Normal Range

Shift tables will be prepared to compare baseline values to the last post-baseline values using a categorization of low, normal, and high values for each laboratory variable.

Low, normal, and high will be defined according to the reference ranges provided by the central laboratory in the following manner:

- Low: values which are below the lower reference range limit
- Normal: values which are within the lower and upper reference ranges
- High: values which are above the upper reference range limit

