
Negative effects on pregnancy or fetus
	
The preclinical testing has projected that the B2A component of AMPLEX is completely eliminated within six weeks of implantation and during that time that circulating B2A levels are quite low. Therefore, the risk of an effect on a fetus is unlikely.
 
However, to avoid this potential risk, female subjects are excluded from the trial if they are pregnant or lactating, or intend to become pregnant during the course of this study.
 
Monitoring of study conduct and safety data will be conducted on an ongoing basis by Sponsor and Data Monitoring Committee, governed by a Charter. If these groups identify any new or unforeseen risks they will notify the Sponsor and render an opinion on potential study modifications/stopping.

Immune response (bodily response against foreign material)
	
Pre-clinical and clinical immunogenicity testing during PREFIX and AMPLEX development have not demonstrated any immune reactions nor development of significant anti-B2A antibody formation.

	
Although remote, based on the established data, this risk is mitigated through single exposure to AMPLEX and the protocol specified assessment of antibody response.
 
Despite this being a remote risk, monitoring of study conduct and safety data will be conducted on an ongoing basis by Sponsor and Data Monitoring Committee, governed by a Charter. If these groups identify any new or unforeseen risks they will notify the Sponsor and render an opinion on potential study modifications/stopping

Elevated liver enzymes (from the B2A peptide)	
Transient excursions in lab values, specifically liver function enzymes, have been noted in the pilot clinical studies conducted in both the treatment and control groups. After extensive consultation with various experts, it was determined that these elevations are largely related to surgery itself, concomitant medications and pre-existing conditions.
 
Despite this being a remote risk, monitoring of study conduct and safety data will be conducted on an ongoing basis by Sponsor and Data Monitoring Committee (DMC), governed by a Charter. If these groups identify any new or unforeseen risks they will notify the Sponsor and render an opinion on potential study modifications/stopping.

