### 6.1.6 Follow-up Visit at 2 Weeks

The visit window is  $\pm$  3 days.

- Physical assessment of hindfoot/ankle, including vital signs
- Collect two blood samples for: 1) non-fasting chemistry and 2) hematology. Additional details for the collection and handling of blood samples are provided in the SRM
- Subject-based Assessment:
  - If subjects are in the ABG group, ask subjects to rate their graft site pain on the VAS
- Record adverse events
- Record concomitant medications

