### 6.1.7 Follow-up Visit at 6 Weeks

The visit window is  $\pm$  14 days.

- Physical assessment of hindfoot/ankle, including vital signs
- Collect three blood samples for: 1) non-fasting chemistry, 2) hematology and 3) immunogenicity testing for B2A antibodies. Additional details for the collection and handling of blood samples are provided in the SRM
- Subject-based Assessment:
  - If subjects are in the ABG group, ask subjects to rate their graft site pain on the VAS

- Collect A/P, lateral and oblique X-rays of the hindfoot/ankle
- Record adverse events
- Record concomitant medications

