#### **7.3.3 Clinical Laboratory Testing**

Routine clinical laboratory tests (hematology and chemistry, including AST, ALT, ALP, GGT, bilirubin and hemoglobin A1c levels), will be performed at screening (Visit 1) and follow-up through 12 weeks. All female subjects of childbearing potential will have urine pregnancy tests performed at the screening (Visit 1) and within 24 hours of the procedure (Visit 2). At the discretion of the Investigator, additional blood samples may be taken for safety reasons to analyze other clinical laboratory endpoints. All blood samples will be analyzed by a central laboratory. Full details regarding sample collection, processing and shipping will be provided in the SRM. The lab results/reports will be provided to the site. If a laboratory result is abnormal, the Investigator will assess if it is clinically significant (CS) or not clinically significant (NCS). Clinically significant laboratory abnormalities are defined as abnormal results requiring treatment or medical intervention and should be recorded as adverse events. The severity of a clinically significant laboratory finding should be recorded as described; however, abnormal laboratory observations classified as NCS do not require an adverse event to be filed.

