10.6.3 Markedly Abnormal Changes

For liver function tests (AST, ALT, ALP, and total bilirubin levels), a summary table will be prepared displaying the proportion of subjects who have at least one post baseline markedly abnormal value (see [Appendix 1](#)). The denominator will be the number of subjects with baseline and at least one post baseline value. The table will also include a break-down by classification of the baseline value (low/normal/high) according to the reference ranges provided by the central laboratory.

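### The only laboratory shift table uses the last post-baseline value, so transient liver-test rises below the marked thresholds, and transient GGT rises, are not counted by arm

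*SAP*

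**What the plan says.** SAP 10.6.2 sets the shift-table rule for every laboratory variable: "Shift tables will be prepared to compare baseline values to the last post-baseline values using a categorization of low, normal, and high values". No other laboratory shift table is planned.

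Protocol 7.3.3 says that routine chemistry and hematology "will be performed at screening (Visit 1) and follow-up through 12 weeks", and it names AST, ALT, ALP, GGT and bilirubin among the tests. The visit sections give the draws. At Week 2 the instruction is "Collect two blood samples for: 1) non-fasting chemistry and 2) hematology"; at Week 6 (and again at Week 12, Protocol 6.1.8) it is "Collect three blood samples for: 1) non-fasting chemistry, 2) hematology and 3) immunogenicity testing for B2A antibodies".

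Three other SAP outputs use laboratory data:
- 10.6.1: "Observed values and changes from baseline for the last post-baseline values will be presented for each laboratory variable", plus descriptive statistics at each time point.
- 10.6.3: "For liver function tests (AST, ALT, ALP, and total bilirubin levels), a summary table will be prepared". It gives the proportion with at least one markedly abnormal value after baseline, broken down by baseline category. The thresholds are in SAP Appendix 1.
- 10.6.4: listings of all values, with out-of-range and markedly abnormal values flagged.

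On the risk itself, Protocol Table 1 has a row for raised liver enzymes that names the B2A peptide as the source. It reports: "Transient excursions in lab values, specifically liver function enzymes, have been noted in the pilot clinical studies", in treatment and control groups alike. In the pregnancy row, the same table says preclinical testing projects that the "B2A component of AMPLEX is completely eliminated within six weeks of implantation".

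**The concern.** Liver-enzyme increase is one of the six increased risks listed in Protocol 1.5, and the protocol describes the earlier signal as transient. A shift table built on the last value cannot display a transient change: it records where each subject ended, not what happened in between. For most subjects it looks at about Day 85, whereas B2A is projected to be gone by about Day 43.

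The protocol attributes the pilot excursions largely to surgery, concomitant medication and pre-existing conditions. Both arms have surgery, so comparing the arms on how many subjects go from normal to high at the early visits would be a direct, simple check of that attribution. If the planned tables do not give that count, the report cannot show it, although the blood samples will have been taken and analysed.

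**Working it through.** This point concerns how a table is defined. The plan states no figure to reproduce, so the check sets the schedule against the output definitions.

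**Step 1. Which draw is the last one.** Scheduled post-baseline chemistry falls on Day 15 (± 3), Day 43 (± 14) and Day 85 (± 14), per Protocol Table 3. For a subject with a Week 12 sample, the last value is that sample or a later unscheduled one (allowed by Protocol 7.3.3). Two of the three scheduled draws then do not enter the shift table. For a subject who leaves early, the last value is Week 2 or Week 6, so the table also mixes time points.

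**Step 2. Where the draws sit against B2A elimination.** Six weeks after surgery on Day 1 is Day 1 + 42 = Day 43.
- Week 2: Days 12 to 18 by protocol and Days 2 to 29 by the SAP Table 1 analysis window. This is inside the projected period.
- Week 6: Days 29 to 57 by protocol and Days 30 to 64 by the SAP window. This straddles the projected limit.
- Week 12: Days 71 to 99 by protocol. This is after it.

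**Step 3. What each output would show.** Illustrative ALT profiles, in multiples of ULN, with high meaning above 1 x ULN and the marked threshold above 3 x ULN:

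| Baseline / W2 / W6 / W12 | Last-value shift (10.6.2) | Worst-value shift | Counted in 10.6.3 |
|---|---|---|---|
| 0.6 / 2.5 / 1.5 / 0.7 | normal to normal | normal to high | no |
| 0.6 / 1.2 / 3.5 / 0.7 | normal to normal | normal to high | yes |
| 0.6 / 4.0 / 1.5 / 0.7 | normal to normal | normal to high | yes |
| 0.6 / 1.0 / 1.0 / 1.5 | normal to high | normal to high | no |

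Only the first profile escapes both categorical laboratory tables. The second and third are picked up by 10.6.3, and the fourth by the existing shift table.

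**Step 4. The resulting gap.** A rise is missing from both categorical tables when it has resolved by the last draw and is in one of these ranges:
- AST or ALT: above 1 and up to 3 x ULN
- ALP: above 1 and up to 1.5 x ULN
- Total bilirubin: above 1 and up to 2 x ULN
- GGT: any size above ULN, because 10.6.3 does not include it

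Protocol 7.3.3 sends clinically significant abnormalities, defined as those needing treatment or medical intervention, to adverse-event recording, and SAP 10.2.2 tabulates them. That leaves the rises not judged clinically significant. They appear only in the by-visit statistics and the listings, and neither counts subjects crossing the reference limit by arm.

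**Step 5. Size.** The documents give no rate. Let p be the share of subjects with a rise that resolves by Week 12, and assume everyone randomised is treated and has a Week 12 sample. Subjects shown as no shift = 320p (AMPLEX) and 160p (ABG):

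| p (assumed) | AMPLEX | ABG |
|---|---|---|
| 2% | 6.4 | 3.2 |
| 5% | 16 | 8 |
| 10% | 32 | 16 |
| 20% | 64 | 32 |

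These are upper limits for the gap in Step 4, since some of these subjects would be counted in 10.6.3 or as adverse events. A difference between arms would be hidden in the same way: with 10% on AMPLEX and 5% on ABG, 320 × 0.10 = 32 and 160 × 0.05 = 8 subjects would all fall in the no-shift cells.

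**The case against.** The strongest reply is that the plan does look at the early draws. SAP 10.6.3 counts a marked AST, ALT, ALP or bilirubin value at any post-baseline time and splits the count by baseline category, so it already gives a between-arm count of subjects going from normal to markedly high. Clinically significant abnormalities in any test, GGT included, become adverse events. Every variable is summarised at each visit, every out-of-range value is flagged in a listing, and the DMC reviews safety data during the trial. Laboratory values are not among the listed safety endpoints, the safety analysis is descriptive, and last versus worst value is a reporting choice that contradicts nothing in the protocol. All of this stands, and it confines the point to the gap in Step 4. It does not close that gap.

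A reader might infer more than the documents support:
- *That the SAP as a whole reports transient liver rises as no change.* It does not, given 10.6.3, the adverse-event route, the by-visit summaries and the listings.
- *That Weeks 2 and 6 are both draws with B2A still present.* Only Week 2 is clearly so. Week 6 lies at or past the projected limit for many subjects, and the projection is preclinical.
- *That the table would miss exactly the pattern seen in the pilot studies.* Protocol Table 1 gives no size, timing or specific enzyme for those excursions and says they occurred in both groups. They may have exceeded the marked thresholds, or resolved before Week 2. The same row calls the risk remote.
- *That this is the only laboratory risk linked to the peptide.* Anti-B2A antibody response is another, and SAP 10.5 covers it.

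**Conclusion.** The point holds in a limited form. The shift table in SAP 10.6.2 shows a liver-test rise that resolves by the last draw as no shift. No other planned table counts, by arm, the subjects whose transient rise was not judged clinically significant and was at or below the marked threshold or in GGT. Because liver-enzyme elevation is a named risk that the protocol labels as coming from the peptide, with a prior signal described as transient, the count is worth having.

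The consequence is a gap in descriptive safety reporting. No success criterion or efficacy inference depends on it. Its numerical size cannot be stated from the documents; the figures in Step 5 rest on assumed rates and on full Week 12 sampling. That the last value is Week 12 for most subjects assumes that most attend that visit and that few have later unscheduled samples.

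**What to change.** In SAP 10.6.2, add a table by arm that shifts baseline category to the worst (maximum) post-baseline category for AST, ALT, ALP, GGT and total bilirubin. Shifts by visit at Weeks 2, 6 and 12 for the same tests would serve equally well and would also show timing. Keep the last-value table as an additional output. Either version covers GGT, which 10.6.3 leaves out. A separate lowest-value shift is not needed for this purpose: SAP Appendix 1 sets no low criterion for the four liver tests that it lists.

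The cost is a short SAP edit and a few descriptive tables from samples already scheduled. There are no new data, no change to visits and no effect on the efficacy analyses.
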